## 6.7 Adjustment for multiplicity, confounders, and heterogeneity

Since we have five treatment arms and therefore five comparisons, we will need to adjust for multiple testing. The treatment arms are correlated,

since they are defined by different doses of the same drug. Thus, standard adjustment for multiple testing using the methods by Bonferroni or Holm are too conservative. Instead, we will use the bootstrap based method suggested by Romano, Shaikh, and Wolf [6], which seamlessly handles correlated tests. The correlation structure of the tests is unknown and we therefore assume that the multiplicativity leads to that the  $\alpha$  decreases from 0.05 to 0.03 in order to declare a significant results (correction by Bonferroni would lead to an  $\alpha$  of 0.01).

We will perform subgroup analyses, where the subgroups are CYP2D6 polymorphism status (excellent, intermediate, poor metaboliser [5]). CYP2D6 polymorphism status will be handled as a categorical fixed effect variable. Other subgroups will likely be studied in non-prespecified analyses.

## 6.8 Interim analysis

We will three months into the study perform an interim analysis on overall dropout level. If the proportion of drop out at three months, we will – at best – have 73% power for our primary analysis (under the same assumptions as described in Section 6.6, apart from the assumption about the proportion of drop outs). In this case, we will increase the number of women the study needs to accrue according to:

$$n_{tot} = 168 \times 6 / (1 - d'),$$

where  $d'$  is the overall proportion of drop outs at three months.

## 6.9 Handling of missing data

The primary analysis will be performed on an ITT basis using the last-observation-carried-forward method. This analysis makes sense from an effectiveness (*de facto*) point of view, however it will likely bias the results towards equivalence for the primary efficacy endpoint (assuming that non-compliance is dose dependant) from an efficacy (*de jure*) point of view (i.e. compared to if no women dropped out from the study). We will therefore perform sensitivity analyses (Section 6.5) where we impute mammographic density 6 months into the study for women who dropped out. Specifically, we will use a multiple imputation protocol where mammographic density at 6 months is imputed using a regression model with density at the time points recorded within the study, age, HRT status, CYP2D6 polymorphisms, and endoxifen levels (at the available time points). The exact choice of multiple imputation model will be done using the study data after database lock using

cross-validation. We will also perform tipping point analyses with respect to the missing data by exploring how extreme the imputation of the missing data will need to be to change the overall conclusion of the trial (see also Section 6.5.1).

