7.1.3 Baseline (Month 0)

Meeting with Investigator

- The investigator will explain the nature and aim of the study, its procedures, possible side effects, requirements and restrictions.
- The woman will sign the ICF before any further study related procedures are performed.
- A woman fulfilling the inclusion and exclusion criteria will be randomised to one of the six treatment arms; tamoxifen 20 mg, 10 mg, 5 mg, 2.5 mg, 1 mg or placebo. All treatments will be on a daily basis for 6 months
- The woman will receive a sufficient amount of IMP in order to take one tablet daily during 6 months
- Screening form, randomization number and other applicable information will be filled in by investigator in the eCRF.
- The participants will be asked if they allow to have two biopsies of the normal breast tissue taken at month 0 and 6. This is optional and complies with a separate study protocol (Protocol: Biopsy Karisma II)

Procedures at baseline

After meeting with investigator when ICF is signed and randomization is performed, the following will be obtained:

- In total 24 ml blood will be collected. The blood will be analysed for tamoxifen metabolites, plasma hormones, plasma proteins, metabolic markers. In addition, DNA will be extracted and plasma aliquots will be biobanked for later analyses.
- The participants will be asked to fill out two web-based questionnaires;
 - The Karma questionnaire including lifestyle factors that influence risk of breast cancer such as age at first birth, breast-feeding, etc., demographic, medical history, quality-of-life, and concomitant medication.
 - o Karisma II baseline questionnaire including general symptoms and tamoxifen related symptoms
- Pregnancy test (urine) will be offered women of childbearing age for safety
- Measurement of weight, length and waist
- Instructions are given on how to use and report events by the Karma-app
- Biopsy of the breast. This is optional and complies with an additional translational study protocol (Protocol: Biopsy Karisma II)

7.1.4 1 month after baseline (+2/-1 weeks)

• Karisma II follow up questionnaire including general symptoms, tamoxifen related symptoms, compliance and health care contact connected to possible side effects

- 7.1.5 3 months after baseline (+/- 2 weeks)
 - Karisma II follow up questionnaire including general symptoms, tamoxifen related symptoms, compliance and health care contact connected to possible side effects

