7.2 Dropouts

Participation in the Karisma II study is voluntary and the study participant may end her participation at any time. There may however be a scientific value to continue investigating the effects of tamoxifen after the participant discontinues her treatment to tamoxifen. Women that drop out after 1 week or more, will therefore be asked to still attend the planed follow-up questionnaires, blood sampling, exit-mammogram and biopsy if applicable. This is however not a mandatory request and the study participant is free to decline. The time limit of exit exams is set to 2 weeks after stop of medication.

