10.6.2 Analysis of the primary endpoint (effectiveness)

The primary analysis will be performed on an intention to treat (ITT) basis.

The results of both papers [4] and [5] showed that a threshold value in mammographic density decrease needs to be exceeded in order for a woman to experience the beneficial effect of tamoxifen. This threshold value was different in [4] compared to [5]. A 10% or greater reduction was needed in [4] whereas a 20% reduction was needed in [5], a difference most likely explained by different methods of measuring mammographic density. However, the proportion of women exceeding this threshold was exactly 48% in both studies, implying that approximately 50% of the women experience the beneficial effect of tamoxifen irrespective of the way mammographic density is measured.

In the Karma II study, we will use area based mammographic density, which was used in both [4] or [5]. With support of the results in [4] and [5], we define the *response threshold* to be the *median decrease* in mammographic density of women in the 20 mg tamoxifen arm (this definition ensures that the same proportion of women exceeds the threshold as observed in

previous studies). Further, we define a *responder* to be a woman whose mammographic density decrease between baseline and 6 months exceeds the response threshold.

Compliance of study drug intake is defined as at least 80% of the prescribed numbers of tablets should be used during time of treatment (i.e. 6 months).

The primary efficacy endpoint is the *proportion of responders* (women with a reduction of mammographic density, from baseline to 6 months). We will test for non-inferiority with respect to the primary efficacy endpoint for groups of women treated with placebo, 1, 2.5, 5, and 10 mg compared to the group of women treated with 20 mg tamoxifen. The non-inferiority margin is defined to be 16.7 percentage points; that is, we define non-inferiority to mean that the fraction of responders is not less than one third of the treated individuals (50% minus 16.7% = 33.3%).

The null hypothesis is thus that the proportion of responders in women treated with placebo, 1, 2.5, 5, and 10 mg is 16.7 percentage points less than those women treated with 20 mg tamoxifen (i.e. the fraction of responders is less than one third).

We will also perform sensitivity analyses where the threshold is varied ± 10 percentage points.

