## 6.1 Populations

The intention to treat (ITT) population consists of all women who were randomized and had eligible measure at baseline and at least one eligible measure post baseline. The Per Protocol (PP) Population consists of all women in the ITT population who remained in the study for at least 6 months (the time period during which Tamoxifen is administered) in the study and who had no significant protocol violations (compliance of study drug intake is defined as at least 80% of the prescribed numbers of tablets should be used during time of treatment). The analyses will be preformed on both ITT and PP, however the primary analyses will be carried out on an ITT basis. ITT analysis will likely bias the results toward equivalence for the primary efficacy endpoint compared to if all participants completed the

study (assuming that non-compliance is dose dependant). The per-protocol analysis, on the other hand, excludes data from patients with major protocol violations and may bias the results in either direction. We will therefore analyse the primary endpoint using both intention-to-treat and per-protocol approaches.

Since we expect around 30% dropout rate, we will also create a dataset where missing data is imputed; the multiple imputation (MP) population (see Section 6.9 for details).

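### The multiple imputation model in SAP 6.9 does not list randomised arm, so the check on the primary analysis itself pulls the arms together; SAP 6.1 should also say that an eligible measure means a density measurement

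*SAP*

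**What the plan says.** **Primary analysis.** SAP 6.9: "The primary analysis will be performed on an ITT basis using the last-observation-carried-forward method". The same section accepts that this is likely to move the result towards equivalence if non-compliance is dose dependent. It answers with MI (also SAP 6.5.1, item 4) and a tipping-point analysis for the missing data.

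**Imputation model.** SAP 6.9 describes a regression for 6-month density on densities recorded in the study, age, HRT status, CYP2D6 polymorphisms and available endoxifen levels. Randomised arm is not listed. The exact model is to be chosen by cross-validation after database lock.

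**ITT set.** SAP 6.1 admits randomised women who "had eligible measure at baseline and at least one eligible measure post baseline". Neither document says what makes a measure eligible. On status, SAP 6.1 says: "The analyses will be preformed on both ITT and PP, however the primary analyses will be carried out on an ITT basis".

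**What is measured, and when.** Post-baseline mammograms are scheduled at month 6 for everyone and at month 12 in Lund (Protocol 5.5, 7.1.6, 7.1.7). The month 1 and month 3 contacts consist of the "Karisma II follow up questionnaire including general symptoms, tamoxifen related symptoms, compliance and health care contact connected to possible side effects". Blood is scheduled at baseline and month 6 only (Appendix 14.3). On drop-outs, Protocol 7.2 says: "Women that drop out after 1 week or more, will therefore be asked to still attend the planed follow-up questionnaires, blood sampling", and also an exit mammogram, within two weeks of stopping. It adds: "This is however not a mandatory request and the study participant is free to decline". The SAP does not mention the exit mammogram.

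**The concern.** In a non-inferiority comparison, anything that makes the arms look alike favours the tested dose. The SAP recognises this for its primary analysis and relies on MI to show what would have been seen without drop-out. An imputation model that does not know a woman's dose gives a drop-out on 20 mg and one on a weak dose values from the same distribution. The check then leans the same way as the analysis it is meant to test, and agreement between the two would reassure too easily.

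A second, smaller gap concerns who is in the primary set. If an eligible measure must be a density image, drop-outs without an exit image are left out. If any post-baseline measure counts, a woman with only a questionnaire would enter with her baseline density carried forward as zero change. Two analysts could build different sets, and this analysis helps select the dose for Karisma III.

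**Working it through.** **1. The plan's own figure.** Inputs from SAP 6.6: one-sided 98.5% limit (z = 2.170), 80% power (z = 0.842), 50% responders in both arms, margin 16.7 points.

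n = (2.170 + 0.842)² × (50×50 + 50×50) / 16.7² = 9.07 × 5000 / 278.89 = 162.6, so 163.

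This is within 3% of the stated 168, and 168 / (1 - 0.30) = 240. The sizing therefore treats the 30% who drop out as not analysed.

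**2. What the listed predictors know about a drop-out with no exit visit.**

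| Predictor | Available value | Carries her dose? |
|---|---|---|
| Density | Baseline only | No |
| Endoxifen | Baseline, before treatment | No |
| Age, HRT status, CYP2D6 | Yes | No |
| Randomised arm | Yes | Yes, but not listed |

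(A Lund drop-out might still attend month 12; that cohort is about 40 women.)

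**3. Expected shrinkage by hand.** If 30% of each arm is imputed from one common distribution, the imputed parts do not differ between arms, so the estimated difference is about 0.70 times the true one:

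- 0.70 × (-23) = -16.1 points
- 0.70 × (-19) = -13.3 points

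**4. Simulation.** Assumptions:

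- 240 women per arm.
- 20 mg follows the Karisma I pattern: a quarter fall by about 50, a quarter by about 20, half do not change. The half-effect dose has half as many women in each falling group.
- Measurement noise SD 5 or 10. The other active arms equal 20 mg.
- 30% missing at random in every arm, no exit visits.
- Ten bootstrap hot-deck imputations, drawn from all six arms pooled or within arm.
- The 20 mg median is recomputed each time; Rubin variance; one-sided 98.5% limit against -16.7 points.

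| Half-effect dose | Mean difference, arm ignored | Mean difference, within arm |
|---|---|---|
| SD 5 | about -16 | about -23 |
| SD 10 | about -13 | about -19 |

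False non-inferiority is about 0.4-2% with arm ignored, against under 1% within arm.

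A second model (normal changes, tested dose exactly at -16.7 points, 30% missing in every arm) gave -11.9 points with arm ignored and -16.6 with arm included. The dose passed in about 3% and under 1% of runs, against a nominal 1.5%.

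**5. Why the pass rate stays low.** The half-width of the limit is 2.170 × √(2 × 0.25/168) = 11.8 points at 168 per arm and 9.9 at 240. To pass, the observed deficit must be no larger than 16.7 - 11.8 = 4.9 points (168) or 16.7 - 9.9 = 6.8 points (240). An average of -13 to -16 is well short of either. The harm is a flattering estimate, not a frequent false claim.

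**6. The two readings of an eligible measure.** Same mixtures, primary analysis, no exit visits; share of runs in which the half-effect dose passes:

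| Analysis set | 30% v 30% drop-out | 30% (20 mg) v 10% |
|---|---|---|
| Density image required | under 1% | under 1% |
| Baseline carried forward | 28-31% | 88-91% |

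With complete data the dose passes in about 0.1-0.6%. Carrying baseline forward matters because only 0.70 × 50% = 35% of the 20 mg arm would then show a true fall, so its median, which is the response threshold, moves to about zero.

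**The case against.** **MI is only a sensitivity analysis, and arm could be added when the model is chosen.** Both are correct. The primary result does not depend on MI, and the SAP does not exclude arm. But the list introduces itself as specific, and choosing a model after lock is a poor time to discover the omission.

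**The SAP already discloses the bias.** It does, in 6.1 and 6.9, and it plans PP, MI and tipping-point analyses. A reader might infer that the bias of carrying values forward was overlooked; the documents do not support that. Its direction is also conditional: the pilot saw no difference in discontinuation between 10 and 20 mg, and the bias would reverse if lower doses lost more women.

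**The alarming figures need the weaker reading.** A reader might infer that a weak dose would pass in 88-91% of trials. That requires questionnaires to count as eligible, no exit attendance, and 30% v 10% drop-out, all together. The endpoint is a density change, Protocol 7.2 supplies an exit image, and the 168-of-240 sizing treats drop-outs as lost. All of this favours the density-only reading. What remains is that the SAP's warning about equivalence makes most sense if blunted values enter the analysis, so one clarifying sentence is fair.

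**A reader might also infer that a rule for discordant ITT and PP results is missing.** Protocol 10.6.2 says "The primary analysis will be performed on an intention to treat (ITT) basis" and SAP 6.1 agrees, so the deciding analysis is named. Requiring both to pass would be a preference.

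**Defining the set does not remove selection.** This stands. The pilot reported more side effects where density fell most. If responders on 20 mg and on the half-effect dose dropped out two or three times as often as non-responders (assumed), with 30% v 10% drop-out and no exit visits, the half-effect dose would pass in 4-6% or 8-12% of runs even under the density-only definition.

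**Conclusion.** The point holds for the imputation model. As listed, it carries no information on dose for drop-outs without an exit visit, and it shrinks a true difference by roughly the missing fraction: about 30% of the deficit when 30% are missing. This weakens the check that the SAP sets against its own stated bias. It does not invalidate the primary analysis and seldom produces a false claim.

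The definition of an eligible measure needs clarifying. The density-only reading is the likelier one, and under it the half-effect dose passes in under 1% with random drop-out and no exit visits. Carrying baseline forward would raise this to about 30% with equal drop-out, and further if drop-out is higher at 20 mg.

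The text is clear on both points. The sizes are indicative: they rest on the assumed mixtures, noise, drop-out pattern and exit attendance, and on a simple fixed 98.5% limit instead of the planned Fisher test with bootstrap step-down. No change to the ITT/PP decision rule is needed.

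**What to change.** **SAP 6.9.** Include randomised arm in the imputation model, or impute within arm. Recompute the 20 mg median threshold in each imputed dataset. Fix the model before unblinding.

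**SAP 6.1.** State that an eligible measure is a mammographic density measurement (6-month or exit image) and that baseline density is not carried forward as a 6-month value. Report by arm the number of randomised women with no post-baseline image.

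**Reporting.** Because that set leaves out drop-outs without an image, and can be biased if drop-out is related to response, show the arm-specific MI and the planned tipping-point results beside the primary result.

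**Cost.** Wording and programming only. The SAP is at version 0.4, and Protocol 10.6 foresees finalisation before database lock. Sample size is unchanged: under this definition, with 30% drop-out in both arms, a truly equal dose passes in about 82% of runs with no exit visits and about 93-94% if all drop-outs attend, so the planned 80% is kept under the assumptions above.

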## 4.2 Study period

Karisma I was a proof of concept study preceding Karisma II. The main reason we conducted the Karisma I study was to investigate time to density change. Radiologists tell us that the time to density change is most probably much shorter than one year, probably only a couple of months. However, the issue of time to density change during tamoxifen therapy has never been addressed.

The results from Karisma I show that, regardless of dose, density decreases within 6 months by about 50% for one quarter of the participants, about 20% for another quarter and not at all for the other participants. This result implicates that tamoxifen intake during 6 months gives a measurable density change of responders; therefore, the treatment period in Karisma II are set to 6 months. From a clinical point of view and for coming study (Karisma III) we will investigate the state of density change and decline of side effects 6 months after tamoxifen cessation in relation to doses.

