## 6.3 Primary analysis: Proportion of responders (efficacy)

The results of both papers [2] and [3] showed that a threshold value in mammographic density decrease needs to be exceeded in order for a woman to experience the beneficial effect of tamoxifen. This threshold value was different in [2] compared to [3]. A 10% or greater reduction was needed in [2] whereas a 20% reduction was needed in [3], a difference most likely explained by different methods of measuring mammographic density. However, the proportion of women exceeding this threshold was exactly 48% in both studies, implying that approximately 50% of the women experience the beneficial effect of tamoxifen irrespective of the way mammographic density is measured.

In the Karma II study, we will use the Stratus method for measuring breast density, which was not used in either [2] or [3]. With support of the results in [2] and [3], we define the response threshold to be the median decrease in mammographic density of women in the 20 mg tamoxifen arm (this definition ensures that the same proportion of women exceeds the threshold as observed in previous studies). Further, we define a responder to be a woman whose mammographic density decrease between baseline and 6 months exceeds the response threshold.

The primary efficacy endpoint is the proportion of responders (women with a reduction of mammographic density, from baseline to 6 months). We will test for non-inferiority with respect to the primary efficacy endpoint for

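### Early exit mammograms at 20 mg lower the responder threshold for every arm, and carrying such values forward lets a dose at the non-inferiority margin pass too often

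*SAP*

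**What the plan says.** SAP 6.3: "we define the response threshold to be the median decrease in mammographic density of women in the 20 mg tamoxifen arm". It adds that "this definition ensures that the same proportion of women exceeds the threshold as observed in previous studies", and "we define a responder to be a woman whose mammographic density decrease between baseline and 6 months exceeds the response threshold". The section does not name the analysis set that supplies the median. The stated guarantee holds only if the median comes from the 20 mg women who are analysed.

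SAP 6.9: "The primary analysis will be performed on an ITT basis using the last-observation-carried-forward method". SAP 6.1 admits to the ITT set any randomised woman who "had eligible measure at baseline and at least one eligible measure post baseline".

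Protocol 7.2: "Women that drop out after 1 week or more, will therefore be asked to still attend the planed follow-up questionnaires". The same request covers an exit mammogram and is voluntary. "The time limit of exit exams is set to 2 weeks after stop of medication".

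SAP 4.2 gives the pilot result: a fall of about 50% in one quarter of women, "about 20% for another quarter and not at all for the other participants". SAP 6.6 plans for 30% drop-out and considers 15% and 10% at a lower dose. SAP 6.1 and 6.9 accept that drop-out which depends on dose will probably push the primary result towards equivalence.

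**The concern.** The comparator's median defines response for all six arms. A 20 mg woman who stops after a few weeks and has an exit image then contributes a short-exposure change to that median. Two things follow.

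- The threshold falls, so smaller decreases count as response in every arm. The 20 mg rate stays near 50% whatever happens, which hides the loss of effect from stopping.
- Carried-forward values replace month-6 values in the responder rates and pull the arms together, more so if fewer women stop at the lower dose.

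Both favour a finding of non-inferiority. The SAP concedes the general direction. It does not say that comparator drop-out also resets the responder definition. The trial exists to choose a dose for a planned study of 8,000 women (Protocol section 4), so a false non-inferiority finding would carry forward.

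**Working it through.** **1. The plan's own figures.** With one-sided alpha 0.015 (z = 2.170), 80% power (z = 0.842), both rates 50% and margin 16.7 points: n = (2.170 + 0.842)² × 0.5 / 0.167² = 163, within 3% of the stated 168; power at 168 is 81.4%. 168 / 0.7 = 240. The 5-point rule in SAP 6.3 also reproduces: 16.7 − 2.170 × √(0.5/168) × 100 = 4.9 points. If all 240 are kept by carrying forward, the same expression gives 6.8 points.

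**2. Inputs.** From the documents: pilot mixture (SAP 4.2), margin (SAP 6.3), 98.5% limit, 240 per arm and drop-out of 30% v 30%, 15% or 10% (SAP 6.6). Not in the documents, so assumed: the pilot summary as point masses at 0, 20 and 50; normal noise with SD 5 (range 3 to 10); the share of stoppers with an exit image; the share of effect present at exit; drop-out unrelated to response; an unpooled limit for the difference.

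**3. Threshold.** Let Q be the upper normal tail. The share of 20 mg women at full exposure above t is

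S(t) = 0.5·Q(t/5) + 0.25·Q((t−20)/5) + 0.25·Q((t−50)/5).

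S(t) = 0.5 gives t = 10.7. With 30% stoppers, all imaged and with no effect at exit, 0.7·S(t) + 0.3·Q(t/5) = 0.5 gives t = 3.7. The reason is simple: only 0.7 × 50% = 35% of the analysed 20 mg women now have a real decrease, so the median falls among the unchanged.

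**4. A dose exactly at the margin.** Scale the share of true decreases by 0.656, so that one third exceed 10.7. At t = 3.7, Q(0.736) = 0.231 and 48.3% of its completers exceed the threshold.

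- 30/30 drop-out: 0.7 × 48.3 + 0.3 × 23.1 = 40.7%, a difference of −9.3 points.
- 30/15: 0.85 × 48.3 + 0.15 × 23.1 = 44.5%, a difference of −5.5 points.

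The standard error is about 4.5 points, so an observed difference above about −6.8 passes. The true shortfall is −16.7.

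**5. Simulated pass rates of that dose (SD 5).** The ranges cover repeat simulations; error is about ±1.5 points at 4,000 runs.

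| Case | Threshold | 30/30 | 30/15 |
|---|---|---|---|
| No drop-out | 10.9 | 2-3% | 2-3% |
| All stoppers imaged, no effect at exit | 3.7 | 32-34% | 61-63% |
| Half imaged, no effect at exit | 5.4 | about 16% | about 30% |
| All imaged, half the effect at exit | 8.3 | 3-8% | 3-8% |

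For the second row, SD 3 to 10 gives about 24-33% and 45-64%.

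**6. What each remedy does (all imaged, no effect at exit).** With the threshold from 20 mg month-6 completers but carried-forward values kept in the rates, the at-margin dose passes in about 20% (30/30) and 57-58% (30/15). The reason is dilution: at 30/30 the difference becomes 0.7 × −16.7 = −11.7 points. A dose with half the true responders (25% v 50%) falls from about 25% to 11% at 30/15. With completers only in both arms, the at-margin dose passes in about 1-4%.

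**The case against.** **Stronger readings that the documents do not support.** A reader might infer that placebo could be declared non-inferior. That needs baseline carried forward as zero change for women with no later image. The threshold then falls to about 1 point, placebo passes in about 17-20% of trials at 30/15, and a half-responder dose in about 80%. SAP 6.1 requires a post-baseline measure, so such women are outside the ITT set. With exit images carried forward, placebo passes in at most about 0.1%. What stands is that last observation carried forward in 6.9 and the ITT definition in 6.1 should be reconciled explicitly. A reader might also take less stopping at lower doses as given. The pilot saw no such difference between 10 and 20 mg, and Protocol 7.5 offers fewer side effects at lower doses as a belief. Equal 30% drop-out still inflates the error, however.

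**Partly handled already.** The SAP plans per-protocol, multiple-imputation, threshold-variation, tipping-point and continuous-endpoint analyses. These could reveal the bias. But imputation, threshold variation and tipping point are labelled sensitivity analyses, nothing requires the per-protocol result to agree, and the imputation model is chosen after database lock.

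**The median is not the main cause when drop-out differs.** This is correct: at 30/15 the completer threshold moves the at-margin pass rate only from 61-63% to 57-58%, and in some exit-effect cases makes it slightly worse. A fix confined to the threshold would not be enough.

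**Completers are selected.** The pilot reported more side effects where density fell most (Protocol section 4). If, as an illustration, 40% of responders and 20% of non-responders stop at 20 mg, responders are 0.30/(0.30 + 0.40) = 43% of completers and their median falls from about 11 to about 6. This limitation stands.

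**The size rests on assumptions.** With half the effect present at exit, the inflation is small.

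**Conclusion.** The concern holds in this form: as written, early exit images at 20 mg lower the threshold for every arm, and carried-forward values dilute the difference. Nothing in the plan lets the per-protocol or imputed result block a non-inferiority claim. The direction follows from the text. The size does not: it runs from slight (3-8% for a dose at the margin) to severe (61-63%), depending mainly on how much effect is present at exit, how many stoppers are imaged, and whether drop-out differs between arms. The exposed case is a moderately inferior dose, not an inert one.

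**What to change.** 1. In SAP 6.3, compute the threshold once, as the median decrease among 20 mg women with an observed month-6 mammogram inside the visit window. Use that fixed value in the ITT, per-protocol and imputed analyses.
2. Declare non-inferiority only if the per-protocol (observed month-6) analysis also clears −16.7 points. Report the imputed analysis alongside, with its model fixed before database lock.
3. Judge the difference in proportions, and drop or restate the arithmetic that turns 50% into a 33.3% floor. With the fixed threshold the ITT 20 mg rate will be about 36-46%; at 36% the margin alone would accept 36 − 16.7 = 19.3%. Item 2 guards against this, because the 20 mg rate among completers stays near 50%.
4. State in SAP 6.1 and 6.9 that women with no post-baseline mammogram are not carried forward from baseline.

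Cost: SAP wording only. The SAP is at version 0.4, and Protocol 10.6 allows it to be finalised up to database lock. Power for a truly equal dose becomes that of the completer analysis, about 78-86%, in line with the planned 80% at 168 per arm. Some bias remains if women who respond at 20 mg are likelier to stop, and the report should say so.
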